Forms			
Title	Statistical Analysis Plan Template		
Code	Version	Effective Date	Page
FRM_ST03_032	02	02 Oct 2017	4 of 26

5.6	Prior and concomitant medications.....	15
5.7	Other baseline characteristics	16
6.	Evaluation of Treatment Compliance and Exposure.....	16
6.1	Compliance to study drug and treatment	16
6.2	Exposure to study drug	16
6.3	Evaluation of pharmacokinetics.....	16
7.	Evaluation of Efficacy	16
7.1	Analysis of primary endpoint.....	16
7.2	Analysis of secondary efficacy endpoints.....	19
7.3	Analysis of exploratory efficacy endpoints	22
7.4	Evaluation of pharmacodynamics.....	22
8.	Evaluation of Safety	23
8.1	Adverse events	23
8.2	Clinical laboratory evaluation.....	24
8.3	Vital signs	24
8.4	ECGs	24
8.5	Physical examination	24
8.6	Other safety evaluations.....	24
9.	Tables, Figures and Listings	24
9.1	Programming conventions	24
10.	Literature	25

Forms			
Title	Statistical Analysis Plan Template		
Code	Version	Effective Date	Page
FRM_ST03_032	02	02 Oct 2017	5 of 26

Abbreviations

ADR	Adverse Drug Reaction
ADaM	Analysis Data Model
AECOPD	Acute Exacerbation Of Chronic Obstructive Pulmonary Disease
AE	Adverse Event
AF	Atrial Fibrillation
ANCOVA	Analysis of Covariance
ATC	Anatomical Therapeutic Chemical
BMI	Body Mass Index
CAT	COPD Assessment Test
CI	Confidence Interval
COPD	Chronic Obstructive Pulmonary Disease
CRF	Case Report Form
CS	Clinically Significant
CV	Cardiovascular
ECG	Electrocardiogram
eCRF	Electronic Case Report Form
EMA	European Medicines Agency
EoT	End of Treatment
FEV1	Forced Expiratory Volume in 1 second
FVC	Forced Vital Capacity
HF	Heart Failure
ICH	International Conference on Harmonisation
ICS	Inhaled Glucocorticosteroids
ITT	Intention-to-Treat
IWRS	Interactive Web Response System
IHD	Ischaemic Heart Disease
LABA	Long-Acting Beta2-Agonist
MedDRA	Medical Dictionary for Regulatory Activities
mMRC	modified Medical Research Council
PP	Per Protocol
PT	Preferred Term
QoL	Quality of Life
SAE	Serious Adverse Event
SAP	Statistical Analysis Plan
SAS	Statistical Analysis System
SD	Standard Deviation

Forms			
Title	Statistical Analysis Plan Template		
Code	Version	Effective Date	Page
FRM_ST03_032	02	02 Oct 2017	6 of 26

SDTM	Study Data Tabulation Model
SoA	Schedule of Activities
SOC	System Organ Class
SOP	Standard Operating Procedure
TEAE	Treatment-Emergent Adverse Event
WHO-DD	WHO Drug Dictionary

Revision History

Document Version	Changes Made	Document Date
0.1	Draft specification based on the following documents: 
 Study protocol (Version 1.0 of 12.03.2018) CRF (Version 1 of 29.06.2018) 	07 Jun 2022
1.0	Final version	22 Nov 2022

Forms			
Title	Statistical Analysis Plan Template		
Code	Version	Effective Date	Page
FRM_ST03_032	02	02 Oct 2017	7 of 26

1. Introduction

This document outlines the statistical methods to be implemented in the analysis of the data of AIFA-ICSLIFE-001 Clinical Trial. The purpose of this plan is to provide general guidelines from which the analysis will proceed, containing a more technical and detailed elaboration of the principal features of the analysis described in the protocol. Any changes to the protocol or Case Report Form (CRF) may necessitate updates to the Statistical Analysis Plan (SAP). In case of deviations from this updated SAP, explanations will be provided in the clinical study report. All final study data will be considered for the analysis regulated by this SAP.

2. Study Objectives

2.1 Primary objective

The primary objective is to demonstrate that in elderly Chronic Obstructive Pulmonary Disease (COPD) patients with one or more cardiac comorbidities (heart failure, and/or ischemic heart disease, and/or atrial fibrillation) who have been recently hospitalized due to an Acute Exacerbation of Chronic Obstructive Pulmonary Disease (AECOPD), 1-years treatment with Long-Acting Beta2-Agonist (LABD)+ Inhaled Glucocorticosteroids (ICS) will prolong the time to first re-hospitalization and/or the death for any cause when compared to 1-years treatment with LABD alone.

2.2 Secondary objectives

Secondary objectives are the following:

- to compare the number of moderate/severe exacerbations of COPD in the two patient groups;
- to compare the number of re-hospitalizations and deaths (all cause) in the two patient groups;
- to compare Quality of Life (QoL) scores measured using the COPD Assessment Test (CAT) and modified Medical Research Council (mMRC) dyspnoea scale between the two patient groups;
- to verify if one year of treatment with combination therapy including ICS increases the risk of pneumonia;
- to compare the number of acute cardiac events in this frail, elderly COPD population;
- to compare the incidence of deaths due to cardiovascular events;
- to compare changes in lung function.

3. Study Design

3.1 General design and plan

 cros nt	Forms			
	Title Statistical Analysis Plan Template			
	Code	Version	Effective Date	Page
	FRM_ST03_032	02	02 Oct 2017	8 of 26

This will be a phase IV, open label, multicenter, randomized pragmatic study in frail elderly patients with COPD. Participants will be treated with either inhaled LABD alone or LABD combined with inhaled glucocorticosteroids. The choice of the specific LABD and ICS to be used will be left to the discretion of the clinical investigator. Thus, the proposed study will be a real-life but randomized study with a 12-month treatment period followed by 3 months follow-up. The center will be considered as a unique stratifying factor, so the study will have a balanced-block center-stratified design.

3.2 Visit Schedule and Visit Windows

Assessments and study visits will be performed as listed in the table below:

Procedure	Screening (up to 10 days before Day 1)	Intervention Period [months]					Follow-up (3 months after last study treatment)
		day 1 (randomization)	3 months	6 months	9 months	12 months (or early withdrawal)	
Visit number	Visit 1	Visit 2	Visit 3	Visit 4	Visit 5	Visit 6	Visit 7
Informed consent	X						
Inclusion and exclusion criteria	X	X					
Spirometry*		X				X	
COPD assessment test (CAT)	X	X	X	X	X	X	X
mMRC dyspnea scale	X	X	X	X	X	X	X
Demography	X						
Physical examination including height and weight	X	X	X	X	X	X	X
Medical history (including substance usage)	X	X	X	X	X	X	X
History of COPD and cardiovascular disease (particularly HF, IHD or AF)	X	X	X	X	X	X	X
Past and current medical conditions	X						
Laboratory assessments	X						
12-lead ECG	X					X	
Chest x-ray	X (Optional)						
Vital signs (blood pressure and heart rate)	X	X	X	X	X	X	
Randomization		X					

 cros nt	Forms				
	Title	Statistical Analysis Plan Template			
	Code		Version	Effective Date	Page
	FRM_ST03_032		02	02 Oct 2017	9 of 26

Procedure	Screening (up to 10 days before Day 1)	Intervention Period [months]					Follow-up (3 months after last study treatment)
		day 1 (randomization)	3 months	6 months	9 months	12 months (or early withdrawal)	
Visit number	Visit 1	Visit 2	Visit 3	Visit 4	Visit 5	Visit 6	Visit 7
Study treatment checked and prescribed		X	X	X	X		
Assessment of symptoms and hospitalizations			X	X	X	X	X
Vaccination check		X	X	X	X		
Adverse event review		X	X	X	X	X	
Serious adverse event review		X	X	X	X	X	X
Concomitant medication review	X	X	X	X	X	X	X

CV = cardiovascular, HF = heart failure, IHD = ischemic heart disease, AF = atrial fibrillation, CAT = COPD Assessment Test, mMRC = modified Medical Research Council.

* Participants with a diagnosis of COPD confirmed by spirometry within the last 3 years, will be immediately eligible for the study after hospital discharge. Participants without a previous spirometric confirmation must have a spirometry test, which must be performed at least 8 weeks after discharge. If confirmed then they can be recruited to the study.

**Participants will be contacted by telephone each month, by the clinical investigator or by a research staff member, to check compliance with the study procedures, vaccination and treatment. Information about any hospitalizations or any unexpected medical events, particularly moderate exacerbations treated with antibiotics and/or steroids will be collected

Paragraph no. 8 “Study Assessments and Procedures” of Study Protocol contains additional details about scheduled visits and time windows.

3.3 Sample size justification

The sample size calculation is based on the superiority criteria of the LABD+ICS group versus LABD alone group in terms of re-hospitalization and/or death. With 464 patients in each group, the percentage of patients experiencing the composite event (re-hospitalization and/or death) is expected to be 9% in the LABD+ICS group and 15% in the LABD alone group. A log-rank test (two-sided 5% significance level) will have 80% power to detect a difference between treatment groups in terms of time to first re-hospitalization and/or death (primary efficacy endpoint). Adjusting for an expected 10% dropout rate, a total of 516 patients per group will need to be randomized.

3.4 Randomization and blinding

All participants will be centrally assigned to randomized study intervention using an Interactive Web Response System (IWRS). Before the study is initiated, the log in information and instructions for the IWRS will be provided to each site.

The center will be considered as a unique stratifying factor, so the randomization will follow a balanced-block center-stratified design.

Study intervention will be dispensed at the study visits summarized in the Schedule of Activities (SoA).

Forms			
Title		Statistical Analysis Plan Template	
Code		Version	Effective Date
FRM_ST03_032		02	02 Oct 2017
		10 of 26	

This is an open-label study; however, the specific intervention to be taken by a participant will be assigned using an IWRS. The site will contact the IWRS prior to the start of study intervention administration for each participant. The site will record the intervention assignment on the applicable case report form.

Potential bias will be reduced by using central randomization.

Since this is an open label study, no unblinding procedures are foreseen.

3.5 Efficacy endpoints

3.5.1 Primary endpoint

The primary efficacy endpoint is the time to first re-hospitalization and/or death (all cause).

3.5.2 Secondary efficacy endpoints

The secondary efficacy endpoints are the following:

- number of moderate/severe COPD exacerbations;
- number of re-hospitalizations and deaths (all cause);
- QoL variation measured as change in CAT total score from baseline to end of treatment period;
- change in mMRC dyspnea score from baseline to end of treatment period;
- number of pneumonia events;
- number of acute cardiac events;
- number of cardiovascular deaths;
- change in FEV1 from baseline to the end of treatment period;
- change in FVC from baseline to the end of treatment period.

3.6 Safety endpoints

The safety endpoints are the following:

- Adverse Events (AEs);
- Vital Signs (blood pressure, heart rate);
- Electrocardiogram (ECG);
- Laboratory parameters;

3.7 Other endpoints

Not foreseen.

4. Statistical Analysis

4.1 General

Descriptive statistics will be provided for all variables in the summary tables for the treatment according to the type of variable summarized.

Forms			
Title	Statistical Analysis Plan Template		
Code	Version	Effective Date	Page
FRM_ST03_032	02	02 Oct 2017	11 of 26

Quantitative variables will be summarised by using n, arithmetic mean, SD, median, minimum and maximum.

Categorical variables will be summarised by using frequency distributions and percentages.

Hypothesis testing will be carried out at the alpha = 0.05 level (two-sided) when comparing treatments. For all inferential analyses, p-value will be rounded to three decimal places. Statistical significance will be declared if the rounded p-value will be less than or equal to 0.05.

All data collected in the CRF will be presented in the listings.

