9.2. Sample Size Determination

The sample size calculation is based on the superiority criteria of the LABD+ICS group vs. LABD alone group in terms of re-hospitalization and/or death. With 464 patients in each group, the percentage of patients experiencing the composite event (re-hospitalization and/or death) is expected to be 9% in the LABD+ICS group and 15% in the LABD alone group. A log-rank test (two-sided 5% significance level) will have 80% power to detect a difference between treatment groups in terms of time to first re-hospitalization and/or death (primary efficacy endpoint). Adjusting for an expected 10% dropout rate, a total of 516 patients per group will need to be randomized.

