9.4.5. Principles of Statistical Analysis

For all inferential analyses, p-values will be rounded to three decimal places. Statistical significance will be declared if the rounded p-value is ≤ 0.05 . No adjustment for multiple testing is planned.

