Time to first re-hospitalization and/or death will be analysed using the Kaplan-Meier estimator. The number of re-hospitalization and/or death-free patients at the beginning of the period, the cumulative number of patients with re-hospitalization and/or death at the end of the period and the probability of being re-hospitalization and/or death-free at the end of the period with the associate 95% CIs will be presented by treatment for the following study periods: (0-12] weeks, (12-24] weeks, (24-36] weeks and (36 weeks-EoT]. The point estimates and the relative 95% CIs will be

Forms			
Title	Statistical Analysis Plan Template		
Code	Version	Effective Date	Page
FRM_ST03_032	02	02 Oct 2017	18 of 26

presented by treatment for the 75th, 50th and 25th percentiles. Comparison between treatments will be performed using the log-rank test stratified by center.

The LABD(s)+ICS group will be declared to prolong time to first re-hospitalization and/or death, compared to the LABD(s) group, if the difference between the two treatments is significantly in favour of LABD(s)+ICS (i.e., the p-value from the log-rank test is ≤ 0.050).

Plots of first re-hospitalization and/or death-free survival by treatment will also be presented.

The following SAS[®] code will be used to provide the Kaplan-Meier estimates for time to first re-hospitalization and/or death:

```
proc lifetest data=dataset TIMELIST=(12 24 36 EOT_A, EOT_B);
time TIME*EVENT(1);
strata CENTER / group=TMT;
run;
```

where TIME represents the time to first re-hospitalization and/or death or time to censoring, EVENT the censoring indicator (1 = censored patient), CENTER the center and TMT the treatment group; EOT_A, EOT_B, have to be replaced by the last time to first re-hospitalization and/or death or last time before EOT for each treatment group (if any).

Time to first re-hospitalization and/or death will also be analyzed using a Cox proportional hazards regression analysis with center and treatment group as qualitative independent variables and age as quantitative independent variables. The inclusion of any other potential confounding factors in the model will be evaluated during the Data Review, verifying the homogeneity of factors distributions among treatment groups.

The number of patients and the number of patients considered in the model will be provided by treatment. P-values of the independent variables based on Wald chi-square test will also be presented.

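### Significance is judged on the p-value after rounding to three decimals, so the nominal two-sided level is 5.05%, not the stated 5% (minor)

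*SAP*

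**What the plan says.** SAP 4.1 makes three statements in sequence. The level is fixed: "Hypothesis testing will be carried out at the alpha = 0.05 level (two-sided) when comparing treatments". Rounding is then imposed: "For all inferential analyses, p-value will be rounded to three decimal places". Finally the decision is attached to the rounded figure: "Statistical significance will be declared if the rounded p-value will be less than or equal to 0.05".

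Protocol 9.4.5 has the same rule, also to three decimals and also for all inferential analyses: "Statistical significance will be declared if the rounded p-value is" at or below 0.05. It adds that no adjustment for multiple testing is planned.

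The primary success rule in SAP 7.1, as in protocol 9.4.6, requires a difference in favour of LABD(s)+ICS such that "the p-value from the log-rank test is ≤ 0.050". That threshold is written to three decimals, and nothing there exempts the log-rank test from the general rule.

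The trial was sized at the exact level. Protocol 9.2 states: "A log-rank test (two-sided 5% significance level) will have 80% power". SAP 3.3 has the same. Neither document plans an interim analysis.

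For reporting, SAP 9.1 separately sets three decimal places for p-values.

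**The concern.** A p-value of 0.0504 is above 0.05, but it becomes 0.050 when rounded and is then declared significant. The threshold actually applied is not the level that the same SAP paragraph and the sample-size sections state. At that boundary, rounding first can only add a significant result and never remove one.

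The rounding in SAP 4.1 is not needed for presentation, because SAP 9.1 already covers that. Its only additional effect is on the decision.

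Two things are at stake. The trial could claim superiority on a p-value above its own stated level. A secondary result could also be called significant while the confidence interval from the same model includes no effect. If the p-value did fall in this narrow range, settling the conflict after the results are known would look outcome-driven, whichever way it went.

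**Working it through.** **Inputs.** Two-sided level 0.05, and p-values rounded to three decimals with significance at a rounded value of 0.05 or less (SAP 4.1, protocol 9.4.5). Sample size (SAP 3.3): "With 464 patients in each group", with event percentages "expected to be 9% in the LABD+ICS group and 15% in the LABD alone group"; 80% power, log-rank test. No interim looks (SAP 4.6).

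**1. The plan's own figure.** Assuming exponential times, HR = ln(0.91)/ln(0.85) = 0.580. Freedman's formula for total events is (1.960 + 0.842)² × [(1 + HR)/(1 − HR)]² = 7.849 × 14.178 = 111.3. Dividing by the sum of the event proportions, 111.3/(0.15 + 0.09) = 463.7, or 464 per group. If events are first rounded up to 112, the result is 467. The plan's figure is thus reproduced at an exact two-sided 5%. The dropout inflation also reproduces: 464/0.9 = 515.6, or 516.

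**2. The level implied by the rule.** A p-value rounds to 0.050 or less when the unrounded value is below 0.0505. If p is uniform under the null hypothesis, the rejection probability is 0.0505. The affected range is strictly above 0.0500, because p = 0.0500 exactly is significant under either rule.

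| | Unrounded p ≤ 0.05 | Rounded p ≤ 0.05 |
|---|---|---|
| Nominal two-sided level | 5.00% | 5.05% |
| Critical \|z\| | 1.9600 | 1.9557 |
| False claim of benefit (half of the level) | 2.500% | 2.525% |
| Power at 464 per group (Freedman) | 80.03% | 80.15% |

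The third row halves the level because success also requires the difference to favour LABD(s)+ICS. Power is Φ(√111.36 / 3.765 − critical z), where 111.36 = 464 × 0.24 events and 3.765 = (1 + HR)/(1 − HR). A simulation of 20 million uniform p-values gave rejection rates of 0.05057 with rounding and 0.05007 without, a difference of 0.0005 as expected.

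**3. How often it would matter.** The rule changes a conclusion only if p lies between 0.0500 and 0.0505. Under the null hypothesis that has probability 0.0505 − 0.0500 = 0.05%, or 5 trials in 10,000. Under the design assumptions it is 80.15% − 80.03%, about 0.12%.

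**4. Confidence intervals.** In the Poisson and ANCOVA analyses (SAP 7.2), the p-value and the 95% interval for the treatment contrast come from the same model. In the Poisson case, an estimate between 1.9557 and 1.9600 standard errors from the null is declared significant, yet its 95% Wald interval (estimate ± 1.960 standard errors) includes no effect. The ANCOVA behaves in the same way with t quantiles. For the primary endpoint the p-value is from the log-rank test stratified by centre. The interval in SAP 7.1 is a Wald interval from a Cox model with centre and age as covariates. The two need not agree at any cut-off.

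**The case against.** The best defence is that this is a disclosed, pre-specified convention. Protocol and SAP state it identically, the primary criterion is written to the same three decimals, and it leaves no discretion once the data are seen. All of that is true. A reader might infer that the SAP departs from the protocol, and it does not. The conflict is between the rule and the level that both documents state.

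A reader might also infer that the trial's actual type I error is 5.05%. The documents do not support that. The stratified log-rank test is asymptotic, and 5.05% is its nominal level. In 200,000 simulated null trials (assuming 39 equal centres of 24 patients, 12% events and no dropout), the size was 4.92% with the unrounded p-value and 4.98% with the rounding rule, with a Monte Carlo standard error of 0.05 points. In that setting the rule does not carry the error above 5%, and its effect is no larger than the approximation error of the test. Other centre sizes could give a different result. This objection stands as a limit on the claim, although the decision rule still contradicts the stated level.

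A third inference, that a primary claim in this range would necessarily be contradicted by its 95% interval, also fails, because that interval comes from the separate Cox model.

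The objection that the effect is practically negligible is largely right, and it sets the severity.

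**Conclusion.** The point holds and is minor. As written, SAP 4.1 and protocol 9.4.5 apply a nominal cut-off of 0.0505 to every inferential test, including the primary log-rank test, where the documents state 0.05. The excess is 0.05 percentage points two-sided, or 0.025 points for a false claim of benefit. Power moves by about 0.1 point, and the required sample size does not change.

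These figures rest on p-values that are uniform under the null hypothesis and, for power, on the plan's 9% and 15% with exponential event times. They describe the nominal rule and do not measure the real error rate of this stratified test. A contradiction with the confidence interval follows for the Poisson and ANCOVA secondary analyses only.

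**What to change.** In SAP 4.1, state that significance is declared if the unrounded p-value is at or below 0.05, and that rounding to three decimals is for display only. Use the same wording for the log-rank criterion in SAP 7.1. Record the clarification in SAP 4.8 as a change from protocol 9.4.5.

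The protocol wording can be aligned at the next amendment, if there is one. An amendment for this alone is not warranted, since protocol 10.1.1 requires ethics committee approval for any amendment.

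The cost is a few sentences in the SAP. Sample size, data collection and statistical methods stay as they are. The change restores the nominal level to 5.00%, with power of 80.0% at 464 per group. It should be made before the results are known.

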4.2 Analysis sets

4.2.1 Randomised population

All randomised patients will be included in the Randomised population. The Randomised population will be considered for descriptive purposes.

4.2.2 Safety population

All randomized patients who receive at least one administration of the study treatment in a given treatment period will be included in the Safety population.

Analysis of safety variables will be performed in the Safety population.

4.2.3 Intention-to-Treat population (ITT)

All randomized patients from the safety population with at least one available post-baseline efficacy evaluation during the treatment period.

Since this is a superiority study, the ITT will be considered the primary analysis set. The primary and secondary efficacy variables will be analysed on the ITT.

The primary efficacy variable will also be analysed on the ITT for sensitivity purposes.

